## 9 Form: AlarmSetup

Screen 1

MY80005-eDiary

23May2017

diary.

First the use of these actions are

Exit

Back

explained visually. Then you will practice using them by yourself.

Use the buttons below to move through the Training. Tap 'Next' to continue.

[figure not shown]

MY80005-eDiary

23May2017

Next >

Message 1

Screen 2 Screen 3 Message 3

Page 21 of 24

Version 3 MY80005-eDiary US English Screen Report 23May2017 Good! A list can be scrolled by placing a Now practice using the scrollable list. Scroll the list and tap '9 days ago'. finger on the list and by swiping the list upward until the needed list item is displayed. Avoid moving your finger on the screen when making a selection. Select first 1 Yesterday Please select first the list item '9 days ago', and tap 2 days ago then the 'Next' button. 3 days ago If you would like to go 4 days ago through the guide pages for the finger scrollable list 5 days ago again, use the 'Back' button 6 days ago to navigate back. 7 days ago Tap 'Next' to continue Tap 'Next' to continue Next > Back Next > Back Screen 4 Screen 5 Message 4 Text can be entered by tapping the text If a mistake is made during typing, box on the screen and then by typing with the displayed keyboard. The characters can be removed by selecting the delete button marked with a 'cross'. If the scrollable list does not scroll when you swipe it, it is not broken. The scrollable list can only be scrolled if there keyboard can be closed by tapping the green tick mark. is more content on the list than can fit on to the screen. X 123 Numbers can be typed by tapping the `123' button. Tap 'Next' to continue Tap 'Next' to continue Tap 'Next' to continue Next Back Next Next Screen 6 Screen 7 Screen 8

Page 22 of 24

Version 3

MY80005-eDiary

US English Screen Report 23May2017 Now practice typing text. Tap the text box below and type something, for example **`medicine 10'**. Did you take your dose of study treatment (tablet) **today**? (Example text) Info 1 Yes Please answer the required question(s) Tap 'Next' to continue Back Next > Back Next > Screen 9 Screen 10 Message 5 How would you rate your worst pelvic pain in the past 24 hours? Thank you! Pelvic pain is defined as localized pain in the lower part of the stomach, below the belly button. Thank you, your training is now complete. 0 1 2 3 4 5 6 7 8 9 10 Back Next > Screen 11 Note: Screen will show latteraly on device Tap 'Next' to continue to your eDiary. Back Next

Page 23 of 24

Screen 12

Version 3 US English Screen Report

MY80005-eDiary 23May2017

## 11 Keyboards

Page 24 of 24

Clinical Study Protocol: MVT-601-3102 Effective: 12-MAR-2018

## Appendix 3. Patient Global Impression of Change and Patient Global Assessments

## Patient Global Impression of Change (Dysmenorrhea)

Compared to when you started the treatment in this study, painful periods are

- 1. Much better
- 2. Better
- 3. A little better
- 4. The same
- 5. A little worse
- 6. Worse
- 7. Much worse

## Patient Global Impression of Change (Nonmenstrual Pelvic Pain)

Compared to when you started the treatment in this study, your pelvic pain when you are **not** having a period (i.e. **not** on your period) overall is

- Much better
- 2. Better
- 3. A little better
- 4. The same
- 5. A little worse
- 6. Worse
- 7. Much worse

Pelvic pain is defined as localized pain in the lower part of the stomach, below the belly button.

#### Patient Global Impression of Change (Dyspareunia)

Compared to when you started the treatment in this study, your pelvic pain when you have vaginal sexual intercourse is

- 1. Much better
- 2. Better
- 3. A little better
- 4. The same
- 5. A little worse
- 6. Worse
- 7. Much worse

□ Not applicable: I have not had vaginal sexual intercourse since starting the study treatment

For this study, we define vaginal sexual intercourse as penetration of any duration.

## **Patient Global Assessment (for pain)**

How would you rate your pelvic pain right now?

Pelvic pain is defined as localized pain in the lower part of the stomach, below the belly button

Absent

Mild

Moderate

Severe

Very Severe

## Patient Global Assessment (for dysmenorrhea during the past 4 weeks)

In the past 4 weeks, did you have your period?

If No: Stop here.

**If Yes:** Continue to the question below.

In the past 4 weeks, how would you rate your pelvic pain on days you had your period (i.e., were on your period)?

Pelvic pain is defined as localized pain in the lower part of the stomach, below the belly button.

Absent

Mild

Moderate

Severe

Very Severe

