#### 9.3.1. Co-primary Efficacy Endpoints

The study has two co-primary efficacy endpoints comparing Group A versus Group C:

- Proportion of responders at Week 24/End of Treatment (EOT) pain assessment period, based on the dysmenorrhea NRS scores recorded in a daily electronic diary and use of rescue analgesics; and
- Proportion of responders at Week 24/EOT pain assessment period based on the NMPP NRS scores as recorded in a daily electronic diary and use of rescue analysesics.

A responder at Week 24/EOT is defined as a patient who had a reduction from Baseline of the determined threshold (or clinically meaningful difference) or greater from Baseline in pain and who did not have an increase in the use of rescue analgesic medications for endometriosis-associated pain during the Week 24/EOT pain assessment period compared with the use in the Baseline pain assessment period.

The Baseline pain assessment period is defined as the period from the date of the first dose of placebo in the Run-In Period through the day prior to the date of the first dose of randomized

Effective: 12-MAR-2018

study drug treatment The Week 24/EOT pain assessment period is defined as the last 35 calendar days immediately prior to and including the last dose of randomized study drug treatment.

Pain data collected in the Baseline pain assessment period will be used as baseline. The Baseline value for dysmenorrhea is defined as the mean NRS scores over the days with menses during the Baseline pain assessment period. The Baseline value for NMPP is defined as the mean NRS scores over the days without menses during the Baseline pain assessment period. The Baseline value for total dose counts is defined as the mean daily dose counts taken during the Baseline pain assessment period multiplied by 35.

The clinically meaningful difference will be determined for NMPP and dysmenorrhea separately (see the Statistical Analysis Plan for details). The anchor-based methods (using PGA for dysmenorrhea and PGA for NMPP as anchors) supplemented with both cumulative distribution function (CDF) and probability density function (PDF) curves will be considered as primary methods to derive the meaningful pain reduction thresholds to be used to define a responder.

Determination of the meaningful pain reduction threshold using PGIC as the anchor will also be explored as supportive.

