### 9.3.2. Secondary Efficacy Endpoints

• Change from Baseline at Week 24/EOT in the EHP-30 Pain Domain scores in the relugolix 40 mg group co-administered with low-dose hormonal add-back therapy for 24 weeks versus placebo;

The change at Week 24/EOT from Baseline in EHP-30 Pain Domain comparing Group A and Group C is a key secondary endpoint to which Type 1 error protection will be extended.

Effective: 12-MAR-2018

To assist in score interpretation, a meaningful within-patient score change threshold for the EHP-30 pain domain will be determined using a similar approach as that for the primary endpoint. A responder at Week 24/EOT based on EHP-30 pain domain scores is defined as a patient who had a reduction of the determined threshold or greater from Baseline using PGA for function as the anchor. Proportion of responders at Week 24/EOT based on EHP-30 Pain Domain scores is a secondary endpoint;

The following secondary endpoints will be assessed comparing Group A with Group C. The Statistical Analysis Plan will specify to which additional secondary endpoints Type 1 error protection will be extended.

- Change from Baseline to Week 24/EOT in the mean dysmenorrhea NRS score;
- Change from Baseline to Week 24/EOT in the mean NMPP NRS score;
- Change from Baseline to Week 24/EOT in the severity scores on the PGA for dysmenorrhea
- Proportion of patients who are better or much better on the PGIC for dysmenorrhea at Week 24/EOT:
- Change from Baseline to Week 24/EOT in the severity scores on the PGA for NMPP.
- Proportion of patients who are better or much better on the PGIC for NMPP at Week 24/EOT;
- Change from Baseline to Week 24/EOT in the mean dyspareunia NRS scores.
- Proportion of patients who are better or much better on the PGIC for dyspareunia at Week 24/EOT;
- Change from Baseline to Week 24/EOT in the mean dyspareunia functional impairment on the sB&B scale:
- Change from Baseline to Week 24/EOT in severity scores on the PGA for pain;
- Proportion of responders at Week 24/EOT based on EHP-30 Pain Domain scores;
- Change from Baseline to Week 24/EOT in function impairment on the PGA for function;
- Change from Baseline to Week 24/EOT in each of the non-pain EHP-30 domains (Control and Powerlessness, Social Support, Emotional Well-Being, and Self-Image);
- Change from Baseline to Week 24/EOT in the mean dysmenorrhea functional impairment on the sB&B scale;

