#### 9.3.2.1. Secondary Efficacy Endpoint Analyses

If the treatment effects for both co-primary endpoints are statistically significant each at 2-sided 0.05 alpha level, the key secondary endpoint of change from Baseline at Week 24 in the EHP-30 Pain Domain scores will be tested comparing the relugolix Group A versus placebo Group C at a 2-sided 0.05 alpha level. The comparison will be performed using a mixed model repeated measures approach with treatment, randomization stratification factors, and treatment by visit interaction included as fixed effects and baseline value included as a covariate and an unstructured covariance. The dependent variable (change from Baseline) for each patient at each visit will be calculated based on the visit windows specified in the Statistical Analysis Plan. Based on this model, the difference in least squares means of change from Baseline between the two groups and corresponding 95% CI and p-value will be presented at Week 24 comparing Group A with Group C.

If this key secondary endpoint is positive, additional secondary efficacy endpoints to which Type 1 error protection will be extended will be tested comparing Group A with Group C using a closed testing procedure to control the familywise error rate at a 2-sided alpha level of 0.05. The details of the closed testing procedure will be provided in the Statistical Analysis Plan, which will be finalized prior to unblinding the trial.

For endpoints evaluating the change from Baseline to Week 24/EOT, treatment comparisons will be performed using a mixed model repeated measures approach with treatment, randomization stratification factors, and treatment by visit interaction included as fixed effects and Baseline value included as a covariate. The dependent variable (change from Baseline) for each patient at each visit will be calculated based on visit windows specified in the final Statistical Analysis Plan. In addition, descriptive statistics will be provided by treatment group and by visit.

For endpoints evaluating proportions, treatment comparisons will be performed using a stratified Cochran-Mantel-Haenszel test.

The daily average sB&B scores for each patient during a specific pain assessment period will be on a continuous scale for the secondary endpoints involving sB&B items with the categories as follows: none = 0, mild = 1, moderate = 2, severe = 3.

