Version 3 MY80005-eDiary 23May2017 US English Screen Report aily Diary For each of the following three Dysmenorrhea (menstrual pain) Pelvic pain symptoms, please select the response that best describes your experience over the past 24 hours. Severe. In bed all day, incapacitation Severe. Requires strong analgesics Moderate. In bed part of day, some loss of work efficiency Moderate. Noticeable pelvic pain Mild. Some loss of work efficiency. Mild. Occasional pelvic pain No pain. No pain associated with No pain. No pelvic pain during past 24 menstruation during past 24 hours. Did not menstruate during the past 24 Back Next > Back Next Back Next > Screen 12 Screen 13 Screen 14 inical Study Medication 11:59 AM inical Study Medication 11:59 AM Daily Diary Deep dyspareunia (pain during intercourse) Did you take your dose of study If yes, please provide: treatment (tablet) today? Time: Severe. Avoids intercourse because of pain Moderate. Intercourse painful to the Yes point of causing interruption 11:59 PM Mild. Tolerated pain No pain. No pain during intercourse No intercourse. No intercourse for other reasons Back Next Back Next Next Screen 15 Screen 16 Screen 17

Page 10 of 24

Page 11 of 24

Screen 21

Back

Back

Screen 20

Save

Screen 22

Effective: 12-MAR-2018

Version 3 US English Screen Report

[figure not shown]
Message 1

MY80005-eDiary 23May2017

Version 3 US English Screen Report

MY80005-eDiary 23May2017

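### Do the dysmenorrhea PGA and sB&B endpoints treat women whose periods stop as ignorable missing data?

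*Protocol*

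**What the plan says.** Three pieces of the protocol meet here.

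- **PGA for dysmenorrhea (Appendix 3).** The form opens with a yes/no question about a period in the past 4 weeks. For a negative answer it directs "If No: Stop here". Section 9.3.2 lists "Change from Baseline to Week 24/EOT in the severity scores on the PGA for dysmenorrhea" among the Group A versus Group C secondary endpoints.
- **sB&B dysmenorrhea (Appendix 2, daily eDiary).** Besides the pain grades and a no-pain answer, the patient may choose "Did not menstruate during the past 24" hours. Section 9.3.2.1 gives the scoring as "none = 0, mild = 1, moderate = 2, severe = 3", with nothing for that extra answer. Change in the mean is also a secondary endpoint.
- **Model (Section 9.3.2.1).** "For endpoints evaluating the change from Baseline to Week 24/EOT, treatment comparisons will be performed using a mixed model repeated measures approach".

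The PGA has a second use. In Section 9.3.1 the co-primary responder thresholds come from "The anchor-based methods (using PGA for dysmenorrhea and PGA for NMPP as anchors"), and "Determination of the meaningful pain reduction threshold using PGIC as the anchor will also be explored as supportive". For the NRS, the same section says "The Baseline value for dysmenorrhea is defined as the mean NRS scores over the days with menses during the Baseline pain assessment period"; it gives no matching sentence for Week 24/EOT.

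**The concern.** Section 2.1 describes medical management of endometriosis as aiming, among other things, at amenorrhea. Section 2.2.4.2 reports amenorrhea in 72.7% of fibroid patients on relugolix 40 mg. Loss of menses should therefore be more common on relugolix than on placebo, and it would be an effect of treatment.

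A likelihood-based repeated-measures model that receives no value for these women represents them by women in the same arm who still bleed. The contrast then describes mainly women still menstruating. If no period is taken to mean no menstrual pain, the benefit is understated on two secondary endpoints. The anchor sample for the dysmenorrhea threshold would also lack a Week 24 value from women whose menses had stopped. If the menses-day average were carried to Week 24/EOT and women without menses days were dropped, a co-primary endpoint would be affected too.

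The protocol does address the parallel case for dyspareunia by restricting that analysis to women with intercourse in both periods. That makes its silence on dysmenorrhea stand out.

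**Working it through.** **1. What is fixed and what is left open**

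| Item | Recorded when there is no menses | Score stated | Said to be missing or excluded |
|---|---|---|---|
| PGA dysmenorrhea | the answer *No* | none | no |
| sB&B dysmenorrhea | the no-menses answer, daily | none | no |
| Dysmenorrhea responder status | daily menstruation entries | details to the SAP (9.3.1) | no; mITT applies (9.2, 9.3.1.1) |

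Section 9 assigns no numbers to the five PGA severity categories either. The PGA endpoint cannot be computed from the protocol alone even for a woman who bled, so its scoring clearly belongs to the SAP. Section 9 leaves detailed methods to that document and requires it to be final before unblinding.

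**2. The plan's own power figure**

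Inputs from Section 9.3.1.3: 200 per arm, 20% dropout, two-sided 0.05, 30% to 35% on placebo, difference 20 points, chi-squared test. Evaluable n = 200 × (1 − 0.20) = 160 per arm.

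Power = Φ{[Δ√n − 1.96√(2p̄(1−p̄))] / √(p₁(1−p₁) + p₂(1−p₂))}

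- 30% v 50%: (2.530 − 1.358) / 0.678 = 1.728, power 0.958
- 35% v 55%: (2.530 − 1.379) / 0.689 = 1.670, power 0.953
- Both endpoints, if independent: 0.918 and 0.907

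The stated figures of at least 95% and 90% reproduce. They concern the responder endpoints; the protocol gives no power for the two change scores.

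**3. Size if the PGA were left missing**

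None of these inputs is in the protocol except 72.7%: PGA scored 0 to 4, Baseline mean 2.7, placebo Week 24 mean 2.0, 5% of placebo women without periods, Week 24 mean m among Group A women still bleeding of 1.0, 1.5 or 2.0, and menses stopping after Week 4 or Week 8. Each cell gives the simulated Group A minus C difference with no-period values missing, then with them scored 0.

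| Amenorrhea in A | m = 1.0 | m = 1.5 | m = 2.0 |
|---|---|---|---|
| 30% | −1.00 / −1.19 | −0.53 / −0.88 | +0.02 / −0.46 |
| 50% | −1.02 / −1.40 | −0.50 / −1.15 | −0.01 / −0.90 |
| 72.7% | −0.97 / −1.63 | −0.49 / −1.51 | +0.01 / −1.35 |

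A hand formula gives nearly the same gaps: (rate in A × m) − (0.05 × 2.0). At 50% and m = 1.5 it is 0.75 − 0.10 = 0.65, against 1.15 − 0.50 = 0.65 simulated. The missing-value estimate barely moves with the amenorrhea rate. A second set of assumed inputs (Baseline 2.8, residual SD 0.9, correlation 0.5) gave gaps of 0.28 to 0.41 at 25%, 0.67 to 0.94 at 50% and 1.01 to 1.40 at 72.7%.

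**4. sB&B**

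Five menses days at severity 2 in a 35-day window average 2.0 over menses days. They average 2 × 5/35 = 0.29 if every other day counts as 0. A convention must be chosen. A woman with any menses day in the window still has scored days.

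**5. The co-primary endpoint**

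Section 9.3.1.1 evaluates responders in the mITT Population, which Section 9.2 defines as all randomized women who took a dose. Excluding women without menses would contradict that. At 50% amenorrhea, exclusion would lower power to about 84% to 86%, but the protocol plans no such analysis.

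The opposite alarm, that scoring these women as responders inflates the difference, also fails. At 50% amenorrhea it reads 0.50 + 0.50 × 0.50 − 0.30 = 0.45. That applies the 50% rate to bleeders only, whereas Section 9.3.1.3 assumes it for the whole arm. Any amenorrheic responders already counted in that rate are then counted twice.

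**The case for a change.** The best case for acting is that the protocol did more than stay silent. It fixed the questionnaire, the score list and the model, and for that model it hands only the visit windows to the SAP by name. It treated the not-applicable case for dyspareunia as protocol content. The four-category sB&B list reads as complete yet omits an answer that the diary collects. The gap would be large and tied to treatment: at 72.7% amenorrhea about 160 × 0.273 = 44 of 160 Group A women would have a Week 24 severity. It also reaches the anchor for a co-primary threshold.

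Much of this is factually right. A rule is needed, and leaving the values missing would be a poor one. It does not follow that the protocol adopts that rule; missing at random is a default supplied by the reader. The dyspareunia sentence narrows the population, and such a departure from the mITT default in Section 9.3 has to be stated. No such narrowing is made for dysmenorrhea. On the anchor, Section 9.3.1 sends threshold details to the SAP and keeps PGIC as support, and the PGIC for dysmenorrhea has no stop rule.

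The obvious remedy also has a price. Scoring no period as no pain credits amenorrhea as pain relief, and for the threshold it would set anchor and pain score by the same rule. That choice of estimand needs the fuller treatment a SAP can give.

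**Conclusion.** No change to the protocol is called for. The gap is real but is an unwritten derivation rule for two secondary endpoints and one anchor analysis. The data needed are already collected, and analysts can supply the rule sensibly before unblinding. The only secondary endpoint the protocol itself names for type I error protection is the EHP-30 Pain Domain.

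If the values were left missing, the likely error is to understate relugolix on the PGA: roughly 0.2 to 0.5 points at 30% amenorrhea and 0.7 to 1.4 at 72.7%. That takes no period as no menstrual pain and rests on assumed means and timing. The documents give no amenorrhea rate with add-back, so the size for Group A cannot be fixed. The likely direction is against the drug, so this is not a route to a false claim of benefit. The co-primary power stands as stated.

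The SAP was not available for this review. A reader who has it need only confirm that it gives a score or a population for women with no menses, and says how they enter the anchor analysis.

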### Patient Global Assessment (for nonmenstrual pelvic pain during the past 4 weeks)

In the past 4 weeks, how would you rate your pelvic pain on days you did not have your period (i.e., were not on your period)?

Pelvic pain is defined as localized pain in the lower part of the stomach, below the belly button.

Absent

Mild

Moderate

Severe

Very Severe

## **Patient Global Assessment (for function)**

How much were your daily activities limited by endometriosis over the last 4 weeks?

Not at all Minimally Moderately Significantly Very significantly

Note: The PGA for dysmenorrhea, the PGA for nonmenstrual pelvic pain, and the PGA for function are administered via paper questionnaires.

Clinical Study Protocol: MVT-601-3102 Effective: 12-MAR-2018

## **Appendix 4. Endometriosis Health Profile - 30**

# ENDOMETRIOSIS HEALTH PROFILE QUESTIONNAIRE (EHP-30) PART 1: CORE QUESTIONNAIRE

DURING THE LAST 4 WEEKS,
BECAUSE OF YOUR ENDOMETRIOSIS, HOW OFTEN HAVE YOU...

		Never	Rarely	Sometimes	Often	Always
1.	Been unable to go to social events because of the pain?					
2.	Been unable to do jobs around the house because of the pain?					
3.	Found it difficult to stand because of the pain?					
4.	Found it difficult to sit because of the pain?					
5.	Found it difficult to walk because of the pain?					
6.	Found it difficult to exercise or do the leisure activities you would like to do because of the pain?					

Please verify that you have *checked one box for each question* before moving on to the next page.

## DURING THE LAST 4 WEEKS, BECAUSE OF YOUR ENDOMETRIOSIS, HOW OFTEN HAVE YOU...

		Never	Rarely	Sometimes	Often	Always
7.	Lost your appetite and/or been unable to eat because of the pain?					
8.	Been unable to sleep properly because of the pain?					
9.	Had to go to bed/lie down because of the pain?					
10.	Been unable to do the things you want because of the pain?					
11.	Felt unable to cope with the pain?					
12.	Generally felt unwell?					
13.	Felt frustrated because your symptoms are not getting better?					
14.	Felt frustrated because you are not able to control your symptoms?					

Please verify that you have *checked one box for each question* before moving on to the next page.

## DURING THE LAST 4 WEEKS, BECAUSE OF YOUR ENDOMETRIOSIS, HOW OFTEN HAVE YOU...

		Never	Rarely	Sometimes	Often	Always
15.	Felt unable to forget your symptoms?					
16.	Felt as though your symptoms are ruling your life?					
17.	Felt your symptoms are taking away your life?					
18.	Felt depressed?					
19.	Felt weepy/tearful?					
20.	Felt miserable?					
21.	Had mood swings?					
22.	Felt bad-tempered or short-tempered?					

Please verify that you have *checked one box for each question* before moving on to the next page.

## DURING THE LAST 4 WEEKS, BECAUSE OF YOUR ENDOMETRIOSIS, HOW OFTEN HAVE YOU...

		Never	Rarely	Sometimes	Often	Always
23.	Felt violent or aggressive?					
24.	Felt unable to tell others how you feel?					
25.	Felt others do not understand what you are going through?					
26.	Felt as though others think you are whining?					
27.	Felt alone?					
28.	Felt frustrated that you cannot always wear the clothes you would choose?					
29.	Felt your appearance has been affected?					
30.	Lacked confidence?					

Please verify that you have *checked one box for each question*.

Clinical Study Protocol: MVT-601-3102 Effective: 12-MAR-2018

